# 2.1.2 Per Protocol Population

The Per Protocol (PP) population will consist of all subjects from the mITT population who are not major protocol violators between baseline and the Treatment Cycle 1, Week 6 visit (inclusive).

The allocation of subjects to the PP population will be finalized and documented prior to unblinding.

The PP population will be analysed using the dose group as randomised, regardless of treatment actually received.

# 2.2 Safety Population

The safety population will consist of all randomised subjects who received at least one injection of study treatment, analysed using dose actually received.

In case a subject has not received the planned dose of 1.6 ml in the study limb the actual study limb dose will be calculated based on the actual volume received.

# 2.3 Screened Population

The screened population will consist of all subjects enrolled.

## 2.4 Randomised Population

The Randomised population will consist of all subjects randomised i.e. all subjects allocated to a treatment group at random.

#### 2.5 Pharmacokinetics

Not applicable.

# 2.6 **Populations of Primary Interest**

For the fixed dose Treatment Cycle 1, the primary population for the efficacy analyses will be the mITT population.

Secondary populations of interest for the efficacy analyses will be the PP population and the Randomised Population.

For the evaluation of efficacy over repeated treatments, analyses per Treatment Cycle will be performed using the available data from all subjects of the mITT population in the specified treatment cycle according to the planned dose for the specified treatment cycle.

The safety analyses of the fixed dose Treatment Cycle 1 will be performed on the safety population.

For the evaluation of safety over repeated treatments, analyses per Treatment Cycle will be performed using the available data from all subjects of the safety population in the specified treatment cycle according to the actual dose received in the specified Treatment Cycle.

# 2.7 Reasons for Exclusion from the Populations

Any major protocol deviation will be described in the Protocol Deviations Document (PDD) and its impact on the membership to each analysis population (i.e. mITT, PP and safety populations) for any subject having experienced it will be specified.

The list of major protocol deviations impacting the PP population membership in the latest version of the PDD will be reviewed during the blind data review meeting (BDRM) held prior to database lock, before any unblinding of treatment groups. If necessary, that list will be updated to include any additional major protocol deviation impacting the PP population membership. PP population will be defined for the fixed dose Treatment Cycle 1 only.

#### **3 STATISTICAL METHODS**

#### 3.1 Statistical Analysis Strategy

The statistical analyses will be performed in accordance with ICH E9 guideline [1] and will be based on the pooled data from the individual study sites, unless otherwise stated.

Statistical analyses will be performed by a Contract Research Organisation CC, under the supervision of the Sponsor's statisticians.

Overall, the analysis strategy is to evaluate efficacy and safety data from the initial fixed dose Treatment Cycle 1, where only the study limb could be treated. In addition efficacy and safety over repeated treatments will be evaluated, using analyses by Treatment Cycle, as described below.

Baseline for all analyses, including by Treatment Cycle, is defined as the last value prior to the initial Study Treatment 1 on Day 1.

#### Fixed dose Treatment Cycle 1

For assessment of efficacy and safety of Dysport 8 or 16 U/kg for the treatment of upper limb spasticity, relative to the minimal dose of 2 U/kg, Treatment Cycle 1 will be evaluated in which a fixed dose was administered to the designated study limb.

Data will be analysed according to the randomised dose (efficacy) or actual dose received (safety) for the study limb in Treatment Cycle 1.

#### Repeat Treatment

For the assessment of efficacy and safety over repeated Dysport treatments, the focus will be on those subjects who received 8 or 16 U/kg in the study limb. Data will be presented by Treatment Cycle and analysed according to the planned dose (efficacy) or actual dose received (safety) in the study limb in the stipulated Treatment Cycle.

As subjects can receive Dysport in the lower limb(s) and non-study upper limb from Study Treatment 2 onwards, safety over repeated Treatment Cycles will also be evaluated using the total body dose of Dysport received in the specified Treatment Cycle.

## 3.1.1 Primary Efficacy Endpoint

The primary efficacy endpoint is the mean change from Baseline to Treatment Cycle 1, Week 6 in MAS score in the Treatment 1 Cycle PTMG (elbow flexors or wrist flexors).

# 3.1.2 Secondary Efficacy Endpoints

The secondary efficacy endpoints are:

- Mean PGA score at Treatment Cycle 1, Week 6.
- Mean GAS score at Treatment Cycle 1, Week 6.

# 3.1.3 Tertiary Efficacy Endpoints

In the following list, the term 'all post-treatment visits' refers to data from each visit at each treatment cycle (Treatment Cycles 1, 2, 3, and 4), unless it is specifically stated that it relates only to visits from the fixed dose Treatment Cycle 1.

Where the term 'except Week 6' is utilised for analyses of Treatment Cycle 1, it only means that this is already a specified primary or secondary endpoint, not that it will not be analysed.

- Mean change from Baseline to all post-treatment visits of Treatment Cycle 1 (except Week 6) in MAS score in the Treatment Cycle 1 PTMG.
- CCI
  Mean change from Baseline to all post-treatment visits in MAS score in each injected muscle group (elbow, wrist and finger flexors) of the study limb.
- CCI

•

•

29/108

#### SAP Final Version 2.0: 19 Oct 2018

Mean change from Baseline to both post-treatment PedsQL scores.

# 3.1.4 Safety Endpoints

The safety endpoints are:

• Treatment emergent adverse events (TEAEs).

- Vital signs (systolic and diastolic BP and HR): absolute values and change from Baseline at each visit to the study centre.
- Body weight and height: absolute values and change from baseline at Week 16 of each treatment and at the EOS/EW.
- Clinical chemistry (including serum ALP total and bone isoenzyme, and HbA1c): absolute values and change from Baseline at Treatment Cycle 1, Week 16 (serum ALP total and bone isoenzyme, and HbA1c only) and at the EOS/EW.
- Presence of antibodies against Botulinum Toxin Type A (BTX-A-Abs) at baseline and at the EOS/EW.
- A 12-lead ECG: absolute values and change from Baseline in ECG parameters and morphology at Treatment Cycle 1, Week 6 and at the EOS/EW.

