6.2 Inclusion Criteria

Subjects must satisfy all of the following inclusion criteria to be eligible for the study:

- (1) Signed informed consent obtained from the child's parent(s)/guardian(s) and, if applicable, a signed assent from the child.
- (2) Be from 2 to 17 years of age, inclusive.
- (3) Body weight of 10 kg or more at the baseline visit.
- (4) Have a diagnosis of CP, as defined by Rosenbaum [9].
- (5) Have increased muscle tone/spasticity in at least one upper limb.
- (6) Have a MAS score ≥ 2 in the upper limb PTMG (elbow flexors or wrist flexors) of the study limb (the limb to be injected in the first treatment) at the baseline visit.
- (7) Be classified as GMFCS Level 1 to 4.
- (8) CCI [REDACTED]

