11.4.4 Safety Evaluation

The safety endpoints of the study are:

- Treatment emergent adverse events.
- Vital signs (systolic and diastolic BP and HR): absolute values and change from Baseline at each visit to the study centre.
- Body weight and height: absolute values and change from baseline at Week 16 of each treatment and at the end of study visit or early withdrawal.
- Clinical chemistry (including serum ALP - total and bone isoenzyme, and glycosylated HbA1c): absolute values and change from Baseline at Treatment 1, Week 16 (serum ALP - total and bone isoenzyme, and HbA1c only) and at the end of study visit or early withdrawal.
- Presence of BTX-A-Abs at baseline and at the end of study visit or early withdrawal.
- A 12-lead ECG: absolute values and change from Baseline in ECG parameters and morphology at Treatment 1, Week 6 and at the end of study visit or early withdrawal.

All safety data will be included in the safety data listings and summary tables will be produced on the safety population. Descriptive statistics will be provided for the safety endpoints.

Adverse Events

Adverse events will be coded using the Medical Dictionary for Regulatory Activities (MedDRA, version in force at the time of database freeze).

All AEs reported during the study will be presented in a listing which will be sorted by treatment group, subject ID, primary system organ class (SOC), preferred term, verbatim text and start date.

Listings of all SAEs, AEs leading to withdrawal and deaths reported during the study will also be presented by treatment group and subject ID.

A TEAE is defined as any AE that occurs during the treatment phase of this study if:

- (1) It was not present prior to the first of intake of study treatment, or
- (2) It was present prior to the first intake of study treatment but the intensity increases during the treatment phase of this study.
- (3) It was present prior to receiving the first dose of study treatment, the intensity is the same but the drug relationship became related during the active phase of the study.

An overall summary table of all AEs will be presented. In summaries of intensity, causality, and causality combined with intensity, subjects may be reported in more than one category in these tables according to how many different levels of intensity and causality are associated to the AEs they experience.

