# 1.2.3 Study Exposure

The overall duration of the study is anticipated to be approximately 4 years and 9 months. Individual subject participation will be approximately 1 year to 1 year and 9 months, depending on the number of treatments administered and the treatment intervals. The 1 year and 9 month follow up period will enable subjects whose first three treatment intervals fall between >16 and  $\leq$ 22 weeks to receive four treatments, therefore providing efficacy data for a minimum of 1 year.

15/108

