3.2.3.4 Vital Signs

Vital signs data (systolic and diastolic BP and HR) will be presented in a listing which will be sorted by subject ID and assessment visit. All abnormal values will be flagged (High (H) or Low (L)).

Baseline values for each treatment group will be defined as the last vital signs measurement collected prior to receiving the initial study treatment on Day 1 of Treatment Cycle 1. For the fixed dose Treatment Cycle 1 the summary table will be presented by Study Limb Dose. The tables for Repeat Treatment will be presented by Total Body Dose and subjects will be assigned to the treatment group in the designated Treatment Cycle according to the study treatment received in that cycle.

For each treatment group, summary statistics will be presented for each scheduled assessment visit, for both actual values and changes from baseline. The number and percentage of subjects with low, normal or high values will also be presented, for each treatment group, at each scheduled assessment. In addition, shift from baseline to tables of the number and percentage of subjects with low, normal or high values will be presented for each treatment group, at each scheduled assessment.

The criteria thresholds for abnormal values are presented in section 8.1.

In addition, body mass index (BMI) will be calculated using age in months at the time of the height and weight assessments. This will be included in the listing, and a shift from baseline table will present the number and percentage of subjects in Less than the 5th percentile, 5th Percentile to less than the 95th percentile, and Equal to or greater than the 95th percentile categories for each treatment group, at each scheduled assessment. The criteria for BMI normal ranges are presented in section 8.2.

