# 8.2 Body Mass Index Normal Ranges

## Table 13 BMI categories

| Weight Status Category     | Percentile Range                                |
|----------------------------|---|
| Underweight                | Less than the 5th percentile                    |
| Healthy weight/ Overweight | 5th percentile to less than the 95th percentile |
| Obese                      | Equal to or greater than the 95th percentile    |

|                 |                       | Boys                                      |                   |                       | Girls                                      |                   |
|-----------------|-----------------------|---|-------------------|-----------------------|--|-------------------|
| Age
(months) | Underweight:
BMI < | Healthy weight/
Overweight:
BMI : I | Obese :
BMI >= | Underweight:
BMI < | Healthy weight/
Overweight:
BMII : I | Obese :
BMI >= |
| 24              | 14.73732              | 14.73732;19.33801                         | 19.33801          | 14.39787              | 14.39787; 19.10624                         | 19.10624          |
| 24.5            | 14.71929              | 14.71929;19.2789                          | 19.2789           | 14.38019              | 14.38019; $19.05824$                       | 19.05824          |
| 25.5            | 14.68361              | 14.68361;19.16466                         | 19.16466          | 14.34527              | 14.34527; $18.96595$                       | 18.96595          |
| 26.5            | 14.64843              | 14.64843; $19.05567$                      | 19.05567          | 14.31097              | 14.31097; $18.87853$                       | 18.87853          |
| 27.5            | 14.61379              | 14.61379; $18.95187$                      | 18.95187          | 14.27728              | 14.27728; $18.79591$                       | 18.79591          |
| 28.5            | 14.57969              | 14.57969;18.85317                         | 18.85317          | 14.2442               | 14.2442; 18.718                            | 18.718            |
| 29.5            | 14.54615              | 14.54615; $18.75949$                      | 18.75949          | 14.21175              | 14.21175; $18.64472$                       | 18.64472          |

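### Height and weight are safety endpoints but are not standardised for age and sex, and the only age-referenced growth output, a three-class BMI shift table, is insensitive to slowed growth in height

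*SAP*

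**What the plan says.** Body weight and height are safety endpoints in protocol 4.2.2 and 11.4.4 and in SAP 3.1.4, always on the same scale. SAP 3.1.4 reads "Body weight and height: absolute values and change from baseline at Week 16 of each treatment and at the EOS/EW". Protocol 11.4.4 reads "Body weight and height: absolute values and change from baseline at Week 16 of each treatment" and adds the end-of-study or early-withdrawal visit; safety endpoints are summarised descriptively. Protocol 6.2 admits children who must "Be from 2 to 17 years of age, inclusive". SAP 1.2.3 states: "Individual subject participation will be approximately 1 year to 1 year and 9 months". The secondary objective is the long-term safety of repeated treatment (protocol 3.2, SAP 1.1.2).

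One growth output is referenced to age. Under SAP 3.2.3.4, "body mass index (BMI) will be calculated using age in months at the time of the height and weight assessments", and "a shift from baseline table will present the number and percentage of subjects in Less than the 5th percentile", a middle class defined in SAP Table 13 as "5th percentile to less than the 95th percentile", and a top class from the 95th percentile up. The limits, by sex and month of age, are in SAP 8.2.

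The SAP allows for age elsewhere: heart rate and blood pressure ranges (8.1), laboratory normal ranges by gender and age where relevant (3.2.3.3), and shift tables for alkaline phosphatase and HbA1c repeated by age group (3.2.3.7). Height and weight have no such provision in the readable text.

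**The concern.** A gain of a given number of centimetres or kilograms means different things at age 3, 9 and 16, and in boys and girls. A raw change pooled over ages 2 to 17 has no expected value to be read against. Most growing children show a positive change whether or not they are growing as fast as they should.

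The BMI table is the only place where age and sex enter, but BMI is a ratio. A child whose height and weight fall behind together can keep the same BMI class.

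What is at stake is how well an endpoint that the sponsor chose serves the long-term safety objective. The documents do not name growth as a known harm of the product, and this point does not claim that it is one.

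**Working it through.** The plan gives no sample size, power or stated figure for growth, so there is no figure of its own to reproduce. Two checks use the documents alone.

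**1. Length of follow-up.** Four cycles of at most 22 weeks give 4 × 22 = 88 weeks, or 20.2 months. This agrees with the stated maximum of 1 year 9 months (21 months, 91.3 weeks).

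**2. What the BMI table shows if growth stops.** Suppose height and weight both stay unchanged for 21 months. BMI is then constant, and only the class limits move. With lower and upper limits L0 and U0 at the start and L1 and U1 after 21 months, the share of the middle class that stays in class is

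share = [min(U0, U1) − max(L0, L1)] / (U0 − L0).

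This is a share of band width, not of children. All limits come from SAP 8.2.

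For boys from 84.5 to 105.5 months, the band goes from 13.72113–19.15236 to 13.91194–20.82733:

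(19.15236 − 13.91194) / (19.15236 − 13.72113) = 5.24042 / 5.43123 = 96.5%.

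| Age, months | Boys | Girls |
|---|---|---|
| 24.5 to 45.5 | 69.4% | 78.2% |
| 48.5 to 69.5 | 100% | 100% |
| 84.5 to 105.5 | 96.5% | 96.0% |
| 120.5 to 141.5 | 91.8% | 92.3% |
| 156.5 to 177.5 | 90.2% | 92.0% |
| 192.5 to 213.5 | 90.6% | 94.3% |

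In the youngest window both limits fall with age (boys: 14.71929–19.2789 to 14.09723–17.88405). The part that leaves the class therefore moves up into the obese class, which points away from a growth problem.

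As an example with assumed sizes, a boy of 84.5 months at 122 cm and 23 kg has BMI 23 / 1.22² = 15.45. With no growth he is still in the middle class at 105.5 months.

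Zero growth is the extreme case. If slower growth leaves BMI between its unchanged value and the value on the child's starting percentile, the share staying in class is at least as large, because both ends of that range lie in the band wherever the zero-growth value does. Complete arrest would also appear in the raw table, as zero change. Partial slowing would still appear there as a gain, with nothing to compare it with.

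**3. Which comparisons remain.** Cycle 1 is randomised 1:1:1 and stratified by age, 2 to 9 and 10 to 17 years (SAP 1.2). From Cycle 2 all children are planned to receive 8 or 16 U/kg, doses may be changed on request (SAP 1.2.1), and safety is tabulated by dose received (SAP 2.6 and 3.2.1.2). Any low-dose column in that phase does not come from randomisation.

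**The case against.** A reader might infer that the plan cannot tell slowed growth from normal growth at all. The documents do not support that.

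- **BMI is age-referenced.** It uses age at each assessment and sex-specific limits, and shifts are shown by treatment group at each scheduled assessment. This stands, but it does not measure height-for-age.
- **Cycle 1 has concurrent randomised arms.** Normal growth should be similar in each, so raw Week 16 change is a fair comparison. Chance imbalance in age is small: assuming ages uniform within each 8-year stratum, balanced strata and 70 per arm, the standard error of a difference in mean age is (8/√12) × √(2/70) = 2.31 × 0.169 = 0.39 years. This stands. However, 16 weeks is short, and 2 U/kg is not an untreated control.
- **Groups A and B are planned to stay on their randomised doses through Cycle 4.** This stands as a contrast between two active doses, diluted by dose changes and by tabulation on dose received. It cannot show an effect common to both.
- **Other safeguards exist.** All safety data are listed by child, clinically significant physical-examination changes become adverse events, and alkaline phosphatase shifts are repeated by age group. These help with individual cases but do not put growth on an age-standardised scale.
- **The tables index is redacted,** so the absence of further growth tables cannot be proved.

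A size in centimetres would need an outside growth curve, which the documents do not give. None is claimed here.

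**Conclusion.** The point holds in this form: in the readable text, height and weight are summarised only as raw value and raw change. The one age-referenced growth output is insensitive to proportionate slowing. From age 4 on, about 90 to 100% of the middle BMI band width stays in class even under 21 months of complete arrest.

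The weakness matters most from Cycle 2, where no low-dose arm is planned and raw change mixes growth with age, sex and follow-up time. The stronger reading, that slowed growth is undetectable under this plan, fails because of the Cycle 1 comparison and the BMI table.

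The percentages rest only on SAP 8.2 and the assumption that height and weight stop together; they describe band width, not numbers of children. No efficacy conclusion is affected. This is an inexpensive improvement to a descriptive safety endpoint, and it is limited to what the redacted documents let one read.

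**What to change.** In SAP 3.1.4 and 3.2.3.4:

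- Keep the raw summaries and add height-for-age and weight-for-age z-scores (BMI-for-age optional), as value and change from baseline, at Week 16 of each cycle and at EOS/EW.
- Use sex and age in months at each assessment, as SAP 3.2.3.4 does for BMI, not the screening age derived in SAP 3.2.13.1. State the rule where local requirements limit the date of birth collected (protocol 7.2.1 lets demographics follow country requirements).
- Name the growth reference. SAP 8.2 cites none, and it holds no height or weight limits.
- Tabulate by treatment group for Cycle 1, and by the dose groups already planned plus overall for the repeat-treatment phase.
- Do not add a z-score cut-off such as a fall of 0.5, which has no basis in the documents, unless it is labelled descriptive only.

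The cost is SAP wording, one added reference, a few derived variables and one table. Height, weight, sex and visit dates are already collected, and no child has an extra procedure. A general-population reference is imperfect in cerebral palsy, so the quantity to read is the change in z-score, not its level. Even then, without a low-dose arm after Cycle 1, a fall in z-score would not by itself separate drug from disease.

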# 3.1.5 Multiplicity

31/108

#### SAP Final Version 2.0: 19 Oct 2018

# 3.1.6 Significance Testing and Estimation

## Fixed Dose Treatment Cycle 1

Apart from tests described in section 3.1.5, all statistical tests performed on the fixed dose Treatment Cycle 1 efficacy endpoints will be conducted, unless otherwise specified, at a two-tailed  $\alpha$  level of 0.05 and each tested Dysport dose group (8 U/kg and 16 U/kg) will be compared to Dysport 2 U/kg separately. Statistical tests will be performed on the efficacy endpoints for Treatment Cycle 1, up to Week 16 (inclusive), no statistical tests will be performed for any additional visits of Treatment Cycle 1 (any visits after Week 16).

# Repeat Treatment

For the analyses by Treatment Cycle no statistical testing will be performed.

## **3.2** Analysis Methods

Unless otherwise specified, all summary tables will be presented by treatment groups defined in the following sections. For data listings, all data will be listed by subject, Treatment Cycle and visit (or assessment date), if applicable.

